6.12.8 Sensitivity Analyses for the Primary Outcome

In addition to the primary and supportive analysis, two planned sensitivity analyses will be performed.

The first sensitivity analysis will mimic the methods Sitbon et al (2015) used in their primary analysis of selexipag in the GRIPHON study. As those authors say, “The primary analysis was an on-treatment analysis with follow-up data censored at the time selexipag or placebo was discontinued.” The first sensitivity analysis will follow this method and censor subjects at the time they stopped study medication.

The second sensitivity analysis, which is really a set of analyses, will explore the impact of censoring and missing data. These analyses will use a tipping point approach, in which subjects will be censored at Day 1, Day 2, ..., Day 90 after stopping study medication in order to explore the effect of various censoring rules on the inference from the study.

Because of the complexity of the primary and secondary outcomes, and the many possible ways that data might be censored or missing, the statistical team will examine the pattern of missing data and censoring for the pooled efficacy variables at the time of the Blind Data Review (see Section 6.11). At that point, armed with the knowledge of the patterns of divergence from full follow-up that actually occur in the trial, the sponsor may add additional sensitivity analyses, which will be described in an addendum to this SAP (completed prior to database lock).

6.13 Key Secondary Analyses

As described in Section, [5.1.2](#), the study has three key secondary outcomes. The following sections describe the plan for analyzing them.

6.13.1 Change from Baseline Six Minute Walk Test at Week 24

Descriptive statistics showing the raw values and changes from baseline for the 6MWT will be presented for each scheduled visit by treatment group.

A longitudinal model with change from baseline as the outcome variable, implemented through SAS PROC MIXED, will be used to analyze the data. The model will include all measurements of 6MWT. Baseline treprostинil use at time of randomization and baseline average 6MWT will be covariates. The model will include terms for the interaction between visit number and treatment. The contrast between treatment groups as Week 24 will be calculated from the model.

```
proc mixed data=(INPUT DATA SET) alpha=0.05;
  class subjid treatment treprostинil_use visitnum;
  model change_in_6MWT = baseline_6MWT treprostинil_use treatment visitnum
  visitnum*treatment /ddfм=kr;
  repeated visitnum / subject=subject type=UN r;
  lsmeans treatment*visitnum/diff om cl;
  run;
```

Note that visit numbers are used as categorical variables, not as continuous measures of time. Note also the use of *om* as an option in the *lsmeans* statement. This option allows the distribution of the categories, as observed in the data, to be used for the computation of the estimates.

Least square (LS) means for baseline-adjusted 6MWT for each treatment group, LS means of treatment group differences with their associated p-values and 95% CIs for both will be summarized and presented.

Multiple imputation, assuming that patients who stop study medication will adopt the experience in the placebo group, will be used to account for missing data. An addendum to this protocol, to be written before the data are unblinded, will present the SAS program to be used for the multiple imputation.

Sensitivity analyses will explore the extent to which multiple imputation of Week 24 data influences the interpretation of the outcome. One sensitivity analysis will assume that all subjects without Week 24 data would have continued on their assigned treatment through the end of the study; another sensitivity analysis will use the longitudinal model described above without any imputation for missing data. Other planned sensitivity analyses will be described in an addendum to this SAP, which will be completed after the Blind Data Review.

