4.3 Study Duration and Dates

As the trial is intended to continue until the specified number of Clinical Worsening Events (113) has occurred, the duration of treatment for individual subjects will vary. The maximum duration of treatment for any individual subject is expected to be 3 years, with the anticipated date for last subject last study visit in Q2 2016.

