After having had 90 days of experience with inhaled treprostinil, a subject who continues to meet the eligibility criteria will be eligible to be randomized. Subjects who consent to the study and are currently taking inhaled treprostinil at the Screening Visit were randomized into the study after determination of eligibility criteria. Subjects are randomized to either esuberaprost or placebo through a centralized system, stratified by use of inhaled treprostinil (current user at the time of the Screening Visit: yes or no)). Following randomization, the subject, study site staff, the sponsor and the EAC all remain blinded to the treatment group assignment.

Baseline assessments are conducted over two consecutive days with Baseline 6MWT performed on each day; the mean value will establish the Baseline value. Subjects return to the study site at Weeks 4, 8, 12 (first Quarterly Visit), and for Quarterly Visits thereafter. During these study visits, subjects undergo all scheduled efficacy and safety assessments as defined by Appendix 1 of the study protocol. Between scheduled study visits, subjects will be contacted by phone to assess for possible clinical worsening events and to record any newly-occurring or changes to AEs or concomitant medications. Phone contact will be made weekly (except during study visit weeks) between Baseline and Week 12 (first Quarterly Visit), then monthly between Quarterly Visits through the end of study participation.

An optional hemodynamic assessment will be offered to subjects at sponsor-approved sites in the US only. Subjects who volunteer to participate in the hemodynamic substudy will undergo a right heart catheterization 0 to 21 days prior to the Baseline Visit (prior to the first dose of IMP) and at the Month 6 Quarterly Visit (\pm 7 days) at peak study drug blood levels (1 to 2 hours, \pm 15 minutes, after administration of Investigational Medicinal Product [IMP; esuberaprost or placebo]).

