3.2.2 Treatment Groups

Subjects who are taking a stable dose of inhaled treprostinil for the required duration and who met all other eligibility criteria are randomized 1:1 to esuberaprost or placebo as described in Section 3.2.4.

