This study will randomize approximately 240 subjects (120 subjects per treatment group). Calculation of the sample size was based on the assumptions listed above. Under those assumptions, an exponential maximum likelihood test of equality of survival curves would require 113 events overall to detect a treatment difference at a power of 90% at a 0.01 two-sided significance level. Given the expected accrual period and follow-up time, an appropriate sample size is 240 subjects. There was no restriction or quota with respect to number of subjects by country.

Study sample size is based on a 0.01 two-sided significance level to provide sufficient power to observe ‘substantial evidence’ of effectiveness within a single clinical study. However, at the time of the analysis, the effect will be tested at a significance level of 0.05 (see Section 6.10). The power at a 0.05 two-sided significance level is 97%.

Sample size calculations were performed with nQuery Advisor 7.0 (2014) and PASS (Hintze, 2013) using sample size methods for the log-rank statistic based on Lakatos & Lan (1992).

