7.1 Extent of Exposure

Exposure to study drug will be calculated as the date of last dose of IMP minus the date of the first dose of IMP plus 1. If the date of last dose of study drug was missing or unknown and the

last drug record had no return date, no assumption will be made for exact exposure. These analyses will include:

- Duration of exposure (in months)
- Number exposed by time (weekly to 3 months, 3-6 months, 6-12 months, 12-24 months, 24-36 months, ≥ 36 months)
- Number exposed by dose (15 μ g, 30 μ g) by time (weekly to 3 months, 3-6 months, 6-12 months, 12-24 months, 24-36 months, ≥ 36 months)
- Maintenance dose during the study (dose subject maintained on IMP after titration period)

Exploratory analyses may be conducted to assess IMP exposure within subgroups (see Sections 6.7.1 and 6.7.2). If appropriate, graphs will display the use of IMP over time.

Similar presentations will be made for inhaled treprostinil use during the study.

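### The 6MWT model in SAP 6.13.1 fits every visit with an unstructured covariance that the last visits probably cannot support over 3 years of follow-up; limit it to visits through Week 24

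*SAP*

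**What the plan says.** SAP 6.13.1 analyses change from baseline in 6MWT with a longitudinal PROC MIXED model. On the data it says "The model will include all measurements of 6MWT". On time it says "Note that visit numbers are used as categorical variables, not as continuous measures of time". The code adds visit-by-treatment terms and Kenward-Roger degrees of freedom, and sets the covariance with "repeated visitnum / subject=subject type=UN r". The contrast at Week 24 is read from this model, and SAP 6.14.1 reads the Week 12 contrast from the same model. The section gives no last visit, no convergence rule and no second-choice covariance.

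SAP 3.1 gives the schedule: "Subjects return to the study site at Weeks 4, 8, 12 (first Quarterly Visit), and for Quarterly Visits thereafter". The study closes when 113 clinical worsening events have occurred. Protocol 4.3 adds: "The maximum duration of treatment for any individual subject is expected to be 3 years". The exposure table in SAP 7.1 ("Number exposed by time (weekly to 3 months, 3-6 months, 6-12 months, 12-24 months" and onward) ends with a category of 36 months or more. Protocol 4.1.1 restricts site start-up and recruitment in the first six months, and SAP 4.1 leaves those months out of the sample-size calculation.

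**The concern.** A visit enters the model as soon as one subject reaches it. With staggered entry and an event-driven close, only the earliest entrants reach the last visits, and the plan keeps that cohort small. An unstructured matrix must estimate a variance for each late visit and its covariance with every earlier one. With too few subjects the late visit is fitted perfectly, its conditional variance goes to zero, and the likelihood has no proper maximum. The software may then fail to converge, or may print a contrast from a singular matrix.

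This endpoint is one of three tested under Simes' procedure in Stage 2 (SAP 6.10.2), so its p-value also enters the joint decision on the other two. An unreliable standard error or denominator degrees of freedom would matter beyond this one result.

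**Working it through.** **1. Planning inputs reproduced.** The documents give no figure for the 6MWT model, so I checked the event rates used to project attendance. SAP 4.1 assumes one-year rates of 45% and 25%. The hazards are −ln(0.55) = 0.598 and −ln(0.75) = 0.288 per year, and the ratio is 0.481. Schoenfeld's formula at two-sided 0.01 and 90% power gives 4 × (2.576 + 1.282)² / (ln 0.481)² ≈ 112 events, against 113 stated. The exponential maximum-likelihood formula gives 116 per group, as in protocol 10.2. With 113 events, power is 0.905 at 0.01 and 0.973 at 0.05, in line with the stated 90% and 97%.

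**2. Size of the matrix.** K visits need K(K + 1)/2 covariance parameters.
- Through Week 24: 4 visits, 10 parameters.
- To 2.5 years (130 weeks, last visit Week 120): 12 visits, 78 parameters.
- To 3 years (156 weeks): 15 visits, 120 parameters.

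**3. Subjects needed.** With monotone follow-up, visit k is regressed on k − 1 earlier visits plus an intercept and a treatment term, which is k + 1 coefficients. A positive-definite maximum needs more than k + 1 subjects: at least 14 at Week 120 (k = 12) and at least 16 at Week 144 (k = 14).

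**4. Subjects expected.** Sample size: "This study will randomize approximately 240 subjects (120 subjects per treatment group"). Accrual is taken as uniform over 1.5 years (78 weeks). Yearly dropout of 0%, 10% and 20% is my assumption, because the documents give no rate for this trial.

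*Follow-up of 2.5 years.* Reaching Week 120 requires entry in the first 10 weeks: 120 × 10/78 = 15.4 per arm, 30.8 in all.
- Subjects stay after an event: 30.8, 24 and 18 for the three dropout rates.
- Subjects leave at an event: 15.4 × (e^(−0.598 × 2.31) + e^(−0.288 × 2.31)) ≈ 12, then 9 and 7.

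*Follow-up of 3 years including the restricted first six months.* I assume that 5–10% of subjects (12–24) enter evenly over the first 26 weeks. Reaching Week 144 requires entry in the first 12 weeks: 12/26 × (12 to 24) = 5.5 to 11.1 before any loss. With dropout, about 3–11 remain if subjects stay after an event and 1–4 if they leave. Even with no loss, early entry would have to reach 16 × 26/(12 × 240) = 14% for the expected count to be 16.

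**5. Chance that some visit has too few subjects** (4,000 simulated trials per scenario; the last column is a separate projection):

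| Scenario | Dropout 0%, 10%, 20% per year | Separate projection |
|---|---|---|
| 2.5 years, stay after event | 0%, 1%, 10% | 0–6% |
| 2.5 years, leave at event | 71%, 92%, 99% | 63–97% |
| 3 years, restricted start (stay or leave) | 92–100% overall | 95–100% |

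**6. Direct REML fits**, 12 simulated trials per scenario at 10% yearly dropout. The fit was singular in 12/12 at 2.5 years if subjects leave, 0/12 at 2.5 years if they stay, and 12/12 at 3 years in both cases (10% early entry).

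**7. With the model limited to Week 24.** There are 4 visits. If subjects leave at an event, Week 24 holds about 196 subjects with no dropout and 177 at 20% dropout. REML was non-singular in 12/12, with the smallest correlation eigenvalue about 0.14–0.20.

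**The case against.** The strongest reply is that failure depends on the scenario. SAP 4.1 bases the sample size on a total of 2.5 years, and SAP 6.4.2 and 6.12 let subjects continue after an endpoint. Protocol 2.1 and 4.1 also run participation to the sponsor's close. On those terms the matrix is estimable in about 90–100% of simulated trials. This stands, and it is why the point is not put as a certainty. It is only part of the picture. Protocol 7.10.1 ends participation at a confirmed event, in conflict with the sections just cited, and SAP 6.4.2 lets subjects decline to continue after an endpoint. The 2.5 years omits the first six months, and both documents foresee about 3 years or more. The SAP is dated September 2018, against a last visit planned for Q2 2016. That hints at longer follow-up, but the documents do not give the close date.

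A reader might infer that visits or covariance would have to be chosen after unblinding. The documents do not support that. Visit counts can be seen in blinded data, SAP 6.2 promises an addendum of data conventions before unblinding, and SAP 6.12.8 plans a blinded look at patterns of missing data. The body of section 6.11 on blinded data review is not in the text available to me, so I do not count it as silent. The addenda described elsewhere cover imputation and sensitivity analyses, not covariance or visit selection.

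A reader might also extend the defect to the Borg and NT-pro-BNP models. SAP 6.14.3 and 6.14.4 specify neither an unstructured covariance nor all measurements, so that does not follow.

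Multiple imputation does not clearly remove the problem. As described, it covers patients who stop study medication, not visits never reached because the study closed, and one planned sensitivity analysis uses the same model without imputation.

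**Conclusion.** The concern holds as a probable estimation failure that can be prevented while the study is blinded. It is near certain at 3 years with few early entrants, likely at 2.5 years if subjects leave at an event, and unlikely (about 0–10%) at 2.5 years if they keep attending. These figures rest on uniform accrual, the planned event rates, the assumed dropout of 0–20% per year and, for 3 years, the assumed 5–10% early entry. The documents give no counts by visit.

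Failure here means a singular or non-converged covariance. A reader might infer that the Week 24 estimate itself would be wrong. Nothing here shows that: the fits did not use PROC MIXED, did not include the imputation step and did not measure a shift in the contrast. What becomes unreliable is the standard error and the Kenward-Roger degrees of freedom behind the p-value. The consequence is also bounded, because this endpoint is formally tested only if the primary endpoint succeeds.

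**What to change.** In an addendum before unblinding, change SAP 6.13.1 so that the model uses the scheduled visits at Weeks 4, 8, 12 and 24 under the unstructured covariance, for both the Week 24 contrast and the Week 12 contrast in 6.14.1. In the same addendum, name a fallback for non-convergence or a non-positive-definite matrix. It should suit unequally spaced visits, for example spatial power by actual week, or compound symmetry, with sandwich standard errors in place of the Kenward-Roger option. Toeplitz or AR(1) by visit index would treat Weeks 8–12 and 12–24 as the same lag and is not suitable.

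If the Borg and NT-pro-BNP models are to be unstructured, state that and apply the same visit limit. While editing the code, align the subject variable, which is named differently in the CLASS and REPEATED statements.

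The cost is a few lines of SAP text. Visits after Week 24 no longer inform the model. With mostly monotone follow-up they add almost nothing to the Week 24 contrast, and they remain in the planned descriptive summaries by visit.

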1.3.1 Treprostinil, Inhaled (Tyvaso®) Background

Inhaled delivery of treprostinil for the treatment of pulmonary arterial hypertension was developed to deliver selective vasodilatory effects to the lung vasculature while minimizing systemic side effects. Inhaled treprostinil was FDA approved (Tyvaso®) in July 2009 (Tyvaso® US Package Insert) and approved in Israel in 2010.

During the development of inhaled treprostinil, a series of acute and chronic Investigator initiated clinical studies were conducted with inhaled treprostinil sodium to optimize the formulation for inhalation, determine dose response, tolerability, and safety and also to evaluate safety and tolerability when combined with other PAH therapies (Voswinckel 2006; Channick 2006). In the acute dosing studies, administration of inhaled treprostinil sodium resulted in pulmonary vasodilation with excellent tolerability at relatively low doses inhaled in a few breaths. In the chronic studies, administration of inhaled treprostinil sodium resulted in sustained improvement of exercise capacity.

A randomized, double blind, placebo controlled, Phase 3 pivotal study (TRIUMPH-I) was conducted to assess the safety and efficacy of inhaled treprostinil. Two hundred thirty-five subjects who were clinically stable on approved background oral PAH therapy (either bosentan or sildenafil) were randomly allocated to receive either placebo or inhaled treprostinil for 12 weeks. The primary efficacy endpoint was change in exercise capacity at Week 12 as measured by 6 minute walk distance (6MWD). At Week 12, patients receiving inhaled treprostinil had a median improvement of +21.6 meters in 6MWD and patients in the placebo group had a median improvement of +3.0 meters. The Hodges-Lehmann placebo corrected median change from baseline in peak 6MWD was +20.0 meters (p=0.00044). This result was supported by secondary measures related to 6MWD, including similar Week 6 results and maintenance of effect on 6MWD improvement at Week 12 trough, which was measured at least 4 hours after the last dose. The most common adverse events in the treprostinil group were cough (54%), headache (41%), and nausea (19%). There were no remarkable treatment related changes in vital signs, physical examination findings, chest x-rays, pulmonary function tests, or clinical laboratory parameters (McLaughlin 2010).

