6.14 Other Secondary Analyses

The study has the following other secondary outcomes:

- Outcomes at 12 weeks change from baseline in the following:
 - 6MWT
 - WHO Functional Class

- Borg Dyspnea Score
- NT-pro-BNP levels
- Outcomes at 24 weeks change from baseline in the following:
 - Borg Dyspnea Score
 - NT-pro-BNP levels
- Total mortality (censored if lost to follow up)

6.14.1 **Change from Baseline in 6MWT at Week 12**

The model used to test the 6MWT at Week 24 (see Section 6.13.1) will be applied to Week 12; however, the contrast at Week 12 will be used instead of the contrast at Week 24.

6.14.2 **Worsening from Baseline in WHO Functional Class at Week 12**

The method described in Section 6.13.3 will be used to analyze the data at Week 12 substituting the phrase “Week 12” for “Week 24”. For the multiple imputation, only baseline variables will be used.

6.14.3 **Change in Borg Dyspnea Score at Weeks 12 and 24**

The Borg Dyspnea Score is an 11 point scale measuring the degree of dyspnea from 0, or “nothing at all”, to 10, or “panic level”. Descriptive statistics of the raw and change from baseline values for Borg Dyspnea Score will be presented for each scheduled visit by treatment group. A score of 11 will be assigned to subjects who died. The Borg score will be treated as a continuous variable.

A longitudinal model will be used to describe the change from baseline in Borg score over time. Contrasts will be calculated at Weeks 12 and 24 to compare the treatment groups with respect to change. The outcome variable will be change from baseline. Independent variables will be treatment, inhaled treprostinil use baseline Borg, visit number, and the interaction of visit and treatment.

Multiple imputation, assuming that patients who stop study medication will adopt the experience in the placebo group, will be used to account for missing data. An addendum to this protocol, to be written before the data are unblinded, will present the SAS program to be used for the multiple imputation.

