Sensitivity analyses will explore the extent to which multiple imputation of Week 24 data influences the interpretation of the outcome. One sensitivity analysis will assume that all subjects without Week 24 data would have continued on their assigned treatment through the end of the study; another sensitivity analysis use the longitudinal model described above without any imputation for missing data. Other planned sensitivity analyses will be described in an addendum to this SAP, which will be completed after the Blind Data Review.

6.14.4 NT-pro-BNP at Weeks 12 and 24

Descriptive statistics of the raw values and changes from baseline NT-pro-BNP will be presented for each scheduled visit by treatment group. Because the parameter is highly skew, the data will be log-transformed before analysis. A longitudinal model will be used to describe log NT-pro-BNP over time. The outcome variable will be the value at each time of measurement, not the change from baseline. Independent variables will be treatment, inhaled treprostinil use, baseline log NT-pro-BNP, visit number, and the interaction of visit and treatment. Contrasts will be calculated at Weeks 12 and 24 to compare the treatment groups with respect to level of the parameter.

These contrasts will be on the log scale. In order to provide summary statistics that are easily clinically interpretable, the estimates may be back transformed to the natural scale and the change from baseline may be calculated as the difference between the mean of the back-transformed estimates and the mean of the baseline value.

Multiple imputation, assuming that patients who stop study medication will adopt the experience in the placebo group, will be used to account for missing data. An addendum to this protocol, to be written before the data are unblinded, will present the SAS program to be used for the multiple imputation.

Sensitivity analyses will explore the extent to which multiple imputation of Week 24 data influences the interpretation of the outcome. One sensitivity analysis will assume that all subjects without Week 24 data would have continued on their assigned treatment through the end of the study; another sensitivity analysis use the longitudinal model described above without any imputation for missing data. Other planned sensitivity analyses will be described in an addendum to this SAP, which will be completed after the Blind Data Review.

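### The 6MWT mixed model holds the baseline slope equal at every visit; a baseline-by-visit term would recover a little precision at Week 24 at almost no cost

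*SAP*

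**What the plan says.** SAP 6.13.1 fits a single PROC MIXED model to the whole 6MWT series: "The model will include all measurements of 6MWT". Visits fall at Weeks 4, 8 and 12 and then quarterly (SAP 3.1), for up to about 3 years (Protocol 4.3). The baseline is the mean of the Day 1 and Day 2 walks (SAP 6.3.1).

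The MODEL statement begins "model change_in_6MWT = baseline_6MWT" and continues with the inhaled treprostinil stratum, treatment, visit and visit-by-treatment. The text agrees with the code: the stratum and "baseline average 6MWT will be covariates", and the only interaction named is visit by treatment: "The model will include terms for the interaction between visit number and treatment". Visit is categorical and the covariance is unstructured: "repeated visitnum / subject=subject type=UN r". Neither text nor code has a baseline-by-visit term, and no reason is given for a common slope.

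The Week 12 contrast in 6.14.1 comes from the same model. The Borg model in 6.14.3 lists its baseline as one term, followed by "visit number, and the interaction of visit and treatment". The NT-pro-BNP model in 6.14.4 does the same: "baseline log NT-pro-BNP, visit number, and the interaction of visit and treatment".

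**The concern.** The model lets visit means, treatment effects and covariance differ by visit, but not the baseline slope. (The stratum term is also held constant, but stratified randomization keeps that factor balanced, so little hangs on it.) With stable variance, the slope of change on baseline is roughly the correlation with baseline minus 1. It is therefore the same at all visits only if that correlation does not decay. Some decay is plausible in a population enrolled for a declining or unsatisfactory response, with 45% of the placebo group expected to worsen within a year (SAP 4.1).

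If it does decay, the fitted slope is a weighted average over visits, and early visits, which vary least, carry much of the weight. At Week 24 the average would be too flat, leaving part of any chance baseline imbalance in the treatment difference and enlarging its variance. The Week 24 6MWT is one of three Stage 2 endpoints, and Stage 3 opens only if at least one of the three is significant (SAP 6.10.2).

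**Working it through.** **The plan's own figures.** The documents give no SD, correlation, effect size or power for the 6MWT. The sample size for the primary endpoint, which fixes the arm size used below, does reproduce. The hazard ratio is ln(0.75)/ln(0.55) = 0.481. The Schoenfeld formula gives 112 events at 90% power and two-sided 0.01 (plan: 113). With 113 events, power at 0.05 is 97.3% (plan: 97%). The exponential maximum-likelihood formula gives 116 per arm, as in the protocol.

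**Inputs.** From the documents: 120 per arm, a baseline averaging two walks, the visit schedule, accrual of 1.5 years and a total of 2.5 years. Assumed: SD of a single walk 100 m; reliability r of 0.92-0.97; correlation of the true walk at lag s of f + (1 - f)exp(-s/τ), with floor f of 0-0.5 and τ of 26-200 weeks; for the staggered case, 20% dropout per year.

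**Formulas.**
- Baseline variance: V = 100²[r + (1 - r)/2].
- Slope of change at visit t: b(t) = 100²·r·ρ(t)/V - 1.
- Common slope: c = (1'Wb)/(1'W1), where W is the inverse of the residual covariance across visits.
- Shift left at Week 24 per 1-SE baseline imbalance: |b(24) - c|·√(2V/120). One SE is about 100·√(2/120) = 12.9 m.
- Variance of the Week 24 contrast, complete data: (2/120)·σ²(24) with visit-specific slopes. The common slope adds the square of that shift.

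**One case in numbers.** Take a moderate decay, with baseline correlation 0.89 at Week 4, 0.75 at Week 24 and 0.38 at Week 156.
- Visits to Week 156: b(24) = -0.23 and c = -0.185. The shift is 0.53 m (unrounded slopes). The SE with visit-specific slopes is 8.49 m, and with the common slope √(8.49² + 0.53²) = 8.51 m. Variance rises by 0.53²/8.49² = 0.4%.
- Same decay, visits stopped at Week 36: c = -0.127 and the shift is 1.26 m. The SE is √(8.49² + 1.26²) = 8.58 m. Variance rises by 1.26²/8.49² = 2.2%.

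**Across the assumed scenarios.**

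| Visits in the model | Variance increase | Shift per 1-SE imbalance |
|---|---|---|
| Complete to Week 156 | 0.1-2.5% (median 0.9%) | 0.2-1.6 m |
| Complete to Week 96 | 0.2-4.1% (median 1.9%) | 0.3-2.2 m |
| Staggered follow-up with dropout | about 0.1-6% (median about 2%) | about 0.1-2.8 m |
| Constant slope | 0 | 0 |

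The common slope was flatter than the Week 24 slope in every decay scenario, so the direction is consistent. With a higher floor of 0.8 and τ of 52 weeks, complete 3-year follow-up gives only 0.3% and 0.3 m.

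**Validity.** A simulation under no treatment effect used 240 subjects, 10 visits, dropout at random with about 30% missing at Week 24, and 400 runs for each of four scenarios. The mean contrast lay between -0.1 and 0.3 m for both models. Rejection rates were 4.8-6.0% with the common slope and 4.5-6.2% with visit-specific slopes. The Monte Carlo SE is √(0.05·0.95/400) = 1.1 percentage points, so these do not differ materially. Model SE ratios (common over visit-specific) were 1.000-1.016.

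**The case against.** A baseline main effect is an accepted, pre-specified choice, and the case that it costs anything rests on a decay the documents do not report. That stands. A reader might infer that the SAP adjusts Week 24 with a wrong slope, but nothing in the documents shows that the slope varies; if it does not, the common slope is exact.

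A reader might also blame fitting one slope across 3 years of visits. The calculation shows the opposite: later visits have steeper slopes and pull the average toward the Week 24 value, so longer follow-up shrinks the loss. Increases above about 6% appear only if visits stop at Week 24 (up to 15%), which the SAP does not plan.

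Setting the leftover metres against the inhaled treprostinil result, where the "placebo corrected median change from baseline in peak 6MWD was +20.0 meters", would also overstate the matter. That is a Week 12 result for another drug against placebo, not this trial's target effect. The leftover is part of ordinary sampling error, in a contrast whose SE is about 5-12 m over these scenarios.

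On cost, an unstructured covariance over 15 visits already needs 15·16/2 = 120 parameters. The interaction would add up to 14 slopes, some at sparse late visits. That is a real but small burden. Finally, none of these calculations includes the planned placebo-based multiple imputation, whose program is deferred to an addendum, so the loss under the full procedure is unknown.

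**Conclusion.** The point holds as a small, nearly free improvement, not as an error that threatens a conclusion. The model does hold the baseline slope constant across visits without saying why. If the baseline correlation decays, the Week 24 contrast is somewhat under-adjusted. At the median of about 2%, the staggered-follow-up loss is worth 0.02·240, or about 5 subjects; at 6% it is worth about 14. Near that upper end, an SE 2.8% larger would lower 80% power to 77.8%.

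Two further inferences are not supported. The first is that the treatment difference is biased: randomization rules that out on average, and type I error is not materially affected. The second is that only Week 24 matters: the same model gives the Week 12 contrast, and Borg and NT-pro-BNP are contrasted at both weeks. For those two outcomes the gain has not been quantified, and NT-pro-BNP is modelled as log level rather than change, so the 6MWT figures do not carry over. All 6MWT figures rest on the assumed SD, reliability and decay.

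**What to change.** Before unblinding:

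- Add `baseline_6MWT*visitnum` to the MODEL statement in SAP 6.13.1, and name the interaction in the text. This also covers the Week 12 contrast in 6.14.1.
- Use the same mean model in the 6MWT multiple-imputation program, which is still to be written in the addendum.
- For consistency, add baseline Borg by visit in 6.14.3 and baseline log NT-pro-BNP by visit in 6.14.4.
- If the sponsor prefers a common slope, say so and give the reason.

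No new data are needed. The cost is one slope per additional visit in each model. The SAP already provides for addenda before unblinding (SAP 6.2 and 6.13.1), so the change has a place to go.
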